OBJECTIVE: To conduct a prospective, sham controlled, double-blinded, interventional crossover trial to compare standard terminal cleaning plus sham PX-UV (control) with standard terminal cleaning plus PX-UV (intervention) with crossover at 12 months, following a 6-month washout period. Outcome measures include the rates of eiHAIs, as well as the recurrence of genetically identical strains of eiHAIs in patients on study units. The study will be conducted in 2 hospitals and 16 hospital units consisting of a total of 379 beds. A total of three PX-UV devices and three sham devices will be used as part of terminal cleaning following each discharge on study units.

Our central hypothesis is that the addition of PX-UV to standard terminal cleaning will be associated with superior infection prevention, resulting in a reduction in the rate of eiHAIs, as well as a reduction in the recovery of genetically identical strains of drug-resistant organisms. **At the conclusion of the proposed project**, novel data will be generated from a rigorously controlled study regarding the effectiveness of PX-UV in reducing eiHAIs in a representative healthcare setting.

Aim 1: To evaluate the impact of PX-UV disinfection on rates of eiHAIs on study units by:

- 1.1. Comparing rates of eiHAIs on a) study units where PX-UV is added to standard terminal cleaning practices to b) units where a sham UV disinfection system is added to standard terminal cleaning.
- 1.2. Comparing Rates of eiHAIs on the same medical ward during each of two 12-month phases of a crossover study (one phase when a PX-UV device is added and one when a sham device is added to standard terminal cleaning).

Method 1: PX-UV Devices will be used following each discharge on study units, with intervention devices emitting germicidal UV on 50% of the units and sham devices not emitting germicidal UV on 50% of the units, with device users and the study team blinded to the device's sham/intervention status. Rates of eiHAIs will be the primary outcome. Other key variables to be evaluated will include: types and quantities of antibiotics administered, hand hygiene compliance, room cleanliness quality monitoring through fluorescent marking, colonization pressure on study units; and co-morbid conditions and demographics of enrolled patients.

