For the 16 units to be studied, over 8 months from December 2014 through July 2015, the average rate of *C. difficile* infections on day 4+ of a patient's hospital stay was 1.3 per 1000 days. Rates of ESBL+VRE+ MRSA + *A. baumannii* are 1.5 times that for *C. difficile*, so the total rate of all four infection types would be 3.2 (=1.3x2.5). The total average daily census on the 16 units was 291. Assuming the average patient stay is 5.2 days, 42.3% of patient days will be day 4+, so the expected number of daily eligible patient days would be 123. For 24 months of intervention the total number of eligible days would be $123 \times 730 = 89,790$, or 44,895 per arm.

If the power for the Poisson model is approximated by that for a binomial test of proportions, and with a final alpha level of 0.049 to take into account one interim analysis, a 31% reduction in eiHAI incidence (from 3.2 to 2.208 per 1000 eligible days) would be detectable with 81% power.

Hospital Unit Selection

Patient care units from two healthcare facilities have been identified for this study based on a relatively high average recovery of eiHAs. These units will be randomized to receive either the intervention or sham PX-UV devices in Phase 1 of the study, and the intervention and sham PX-UV devices will switch in Phase 2 of the study. The protocol for use of the devices is outlined below.

Clinical Sites

Two DMC acute-care hospitals are being proposed for this project, Sinai-Grace Hospital (SGH) and Detroit Receiving Hospital (DRH). SGH is a 383-bed hospital, and DRH is a 248-bed hospital. The study will be conducted in eight hospital units in SGH and eight hospital units in DRH, including two medical intensive care units (ICUs), two surgical ICUs and 12 non-ICU medical-surgical wards. The 16 study units include a total of 379 beds. During the 24-month study intervention period, we anticipate that 40,852 total patients will be cared for on study units accounting for 89,790 eligible patient days out of a total of 212,430 patient days. If past experience continues unchanged, during the 24-months of intervention, 287 eiHAs attributable to these units would be observed.

Devices will be deployed on these study units with the sham and intervention devices split evenly between SGH and DRH. Within each study site, the types of devices (PX-UV vs sham) will be assigned randomly to the units in Phase 1 and then switched in Phase 2.

Patient Selection

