Analyzing the isolate to library: The isolate sequencing will be interpreted by an experienced microbiologist who will be masked to all clinical, epidemiological and microbiological study information. A reference isolate will be defined initially to compare subsequent isolates to the reference isolates for mapping the clonal spread of an isolate. The genome data will be analyzed to identify single-nucleotide polymorphisms (SNPs) and insertions or deletions. Then reference isolates will be compared to subsequent isolates for mapping clonality of the isolates to define the strain relatedness, and to define any repetition of a particular strain over a given period of time. Further, we can also define if an intervention such as pulsed-xenon disrupts the repetition pattern of strains and compare it other intervention such as manual disinfection.

Statistical Analysis

Aim 1. The primary analysis will use a Poisson regression model to compare PX-UV disinfection with sham disinfection. Analysis will begin with testing for a carryover effect, but the long 6-month washout is expected to make carryover unlikely. An interim analysis for efficacy will be made after the first 12-month intervention period using an O'Brien-Flemming boundary, the trial may be halted for efficacy if a chi square statistic of 8.78 or greater is observed for the interim test ($p \leq 0.003$). With the interim analysis, the p-value for the test at end of the study will need to be 0.049 or lower to be significant. The primary regression model will include patient age, sex, race and indicator variables for co-morbid conditions. Secondary analysis will summarize and compare study arms (and periods) on: administered antibiotic doses and types, hand hygiene compliance, room cleanliness quality (monitoring through fluorescent marking) and eiHAI colonization pressure.

Aim 2 The frequencies of genetically identical strains of eiHAIs in the selected units will be summarized descriptively with regards to timing, location and clinical strain characteristics.

Study Timeline

ACTIVITY TO ADDRESS STUDY AIMS	Year 1				Year 2				Year 3				Year 4				Year 5	
Quarter	1	2	3	4	1	2	3	4	1	2	3	4	1	2	3	4	1	2
IRB, training of environmental services staff	X	X	X	X		X				X				X				X
Phase 1 of crossover			X	X	X	X												
Wash-out period							X	X										
Phase 2 of crossover									X	X	X	X						
Laboratory analysis						X	X	X					X	X	X			
Data analysis and manuscript preparation									X	X	X			X	X	X	X	X

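### Units are randomised within hospital but not by ICU versus ward, so the Phase 1 efficacy look is exposed to a chance ICU imbalance that costs nothing to prevent

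*Combined protocol and SAP*

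**What the plan says.** All of this comes from the combined protocol and SAP.

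- **Units (Clinical Sites).** The two hospitals contribute eight units each. The mix across all 16 is described as "including two medical intensive care units (ICUs), two surgical ICUs and 12 non-ICU medical-surgical wards". The number of ICUs in each hospital is not given.
- **Allocation (Clinical Sites; Specific Aims, Method 1).** "Within each study site, the types of devices (PX-UV vs sham) will be assigned randomly to the units in Phase 1", with a switch in Phase 2. The ratio is even, "with intervention devices emitting germicidal UV on 50% of the units". Hospital is the only restriction on the randomisation that is described.
- **Interim look (Statistical Analysis, Aim 1).** "An interim analysis for efficacy will be made after the first 12-month intervention period". The trial may be halted for efficacy if the chi-square reaches 8.78.
- **Model (same section).** A Poisson regression with patient age, sex, race and co-morbidity indicators. No unit, unit-type, hospital or phase term is listed.
- **Protection claimed (Use of crossover design).** Each unit is to be observed under both devices and so compared with itself.

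**The concern.** With only 16 randomised units, a simple draw within hospital can easily place more ICUs in one arm than in the other. If ICUs and wards differ in eiHAI rate, that imbalance alone produces an apparent device effect.

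The crossover is the plan's answer to differences between units, but it works only once both phases are complete. At the end of Phase 1 every unit has had one device, so the comparison is between different units. That is also the point at which the trial may be stopped. A false stop would end the study before the within-unit comparison on which the design rests had been made.

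**Working it through.** **1. The plan's own figure.** Inputs from Sample size estimation: 3.2 and 2.208 per 1000 eligible days, 44,895 days per arm, two-sided alpha 0.049 (z = 1.969).

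- Standard error = √[(0.0032×0.9968 + 0.002208×0.997792)/44,895] = 0.000347.
- z = 0.000992/0.000347 = 2.86, and 2.86 − 1.969 = 0.89, which gives power 81.4%.

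This agrees with the plan: "a 31% reduction in eiHAI incidence (from 3.2 to 2.208 per 1000 eligible days) would be detectable with 81% power". The figure does not depend on how units are allocated and is not in question here. The boundary of 8.78 corresponds to p = 0.0030 two-sided, or 0.15% in the efficacy direction.

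**2. Chance of an uneven ICU split.** Assume two ICUs per hospital, and four of eight units per arm in each hospital.

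- One hospital: P(ICUs split 1:1) = 2×C(6,3)/C(8,4) = 40/70 = 4/7. P(both in a given arm) = C(6,2)/C(8,4) = 15/70 = 3/14.
- Both hospitals: P(2:2 overall) = (4/7)² + 2×(3/14)² = 0.327 + 0.092 = 0.418, so P(uneven) = 58%.
- P(all four in one arm) = 2×(3/14)² = 9%.
- With 3 + 1 ICUs by hospital these become 57% and 7%. With 4 + 0 they become 49% and 3%.

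**3. Apparent Phase 1 effect with no true effect.** Assume an ICU has 0.7 of a ward's eligible days (ICU share 2.8/14.8 = 19%) and twice the ward rate.

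- 4:0 split: (4×0.7×2 + 4)/(4×0.7 + 4) = 9.6/6.8 = 1.41 in the arm with the ICUs, against 1.00. If PX-UV has no ICU, the null rate ratio is 1/1.41 = 0.71.
- 3:1 split: 9.2/7.1 = 1.296 against 8.4/7.7 = 1.091. The null rate ratio is 0.84 if PX-UV has the single ICU.
- ICU day shares of 15–25% give 0.67–0.74 and 0.82–0.86 respectively.

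**4. False crossing of 8.78 in the efficacy direction.** Simulation with no true effect and two ICUs per hospital. Phase 1 events = 44,895×3.2/1000 ≈ 144. ICU size is 0.7 of a ward, the CV of unit rates within type is 0.3, and the Poisson test is unadjusted.

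| ICU rate ÷ ward rate | Not stratified | Stratified |
|---|---|---|
| 1.5 | 2.0% | 1.4% |
| 2 | 3.7% | 1.4% |
| 3 | 8.5% | 1.6% |

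At a ratio of 1 the two allocations do not differ. Repeat runs moved these figures by about 0.2 percentage points or less. At a ratio of 2, the SD of the unadjusted Phase 1 log rate ratio falls from 0.28 to 0.23 with stratification.

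**5. Adjusting in the analysis instead.** At a ratio of 2, two-sided crossing is about 7.4% with unstratified allocation and an unadjusted test. It is about 2.7% with stratified allocation and the same test. It is also about 2.7% with unstratified allocation and a test stratified by ICU/ward.

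**6. Final analysis.** A stable ICU/ward difference cancels, and the null rate ratio is 1.00 for every split. Now suppose ICU rates fall 30% between phases while ward rates stay flat (rate ratio 2, ICU share 15–25%). The null rate ratio is then 0.94–0.96 or 1.04–1.07 for 1:3 or 3:1 splits, and 0.88–0.92 or 1.09–1.14 for 0:4 or 4:0.

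**The case against.** The strongest reply has four parts.

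- **The crossover deals with unit type.** For the final analysis this stands, as far as stable differences go. It does not cover the interim look.
- **The key input is missing.** The documents report no ICU or ward rate and no ICU share of eligible days. The units were chosen for relatively high recovery of these organisms, which may narrow the contrast. Adjustment for age and co-morbidity may absorb part of it. This stands: the size is conditional, and it is zero if the rates are equal.
- **A covariate would do.** A reader might infer that an imbalance, once drawn, is beyond repair. It is not. Wards remain in both arms even when all four ICUs fall together, and a test stratified by unit type gives about the same false-crossing rate as stratified allocation. But the plan lists no such term, so the protection is available and not yet in place.
- **Most of the remaining error has another source.** A reader might infer that stratifying brings the interim error back to nominal. With a within-type CV of 0.3, about 1.4% remains in the efficacy direction against a nominal 0.15%. That comes from between-unit variation that the Poisson test ignores, which is a separate issue.

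Two larger figures also need care. The chance that at least one hospital has both ICUs in one arm is 1 − (4/7)² = 67%, but this counts draws in which the two hospitals offset each other. Two-sided crossing rates overstate the risk of a false stop, because the plan allows halting for efficacy only.

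**Conclusion.** The point holds as a gap in the allocation scheme and the interim model. An uneven ICU split is roughly as likely as not, or somewhat more so (49–58%, depending on how the ICUs are distributed), and nothing listed in the plan absorbs it at the one look the crossover does not protect. If ICU rates are 1.5 to 3 times ward rates, unstratified allocation raises the chance of a false efficacy crossing from about 1.4–1.6% to 2.0–8.5%. These figures rest on assumed ICU rates, ICU size, within-type variation and ICUs per hospital, and on a test without patient covariates.

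A reader might go further and infer that the final result is biased by unit type. The documents do not support that. It would take a change between phases specific to ICUs, together with an uneven split. Nothing in the documents points to such a change, and the resulting bias would be modest in the commoner 3:1 splits. The stated 81% power is unaffected. This is a no-cost improvement rather than an error in the plan's figures.

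**What to change.** Before Phase 1, randomise ICUs and wards separately within each hospital. With two ICUs per hospital, assign one ICU and three wards to each sequence. Constrain the draw so that the two medical ICUs go to different sequences and the two surgical ICUs likewise. If each hospital has one of each type, this still leaves 2×20×20 = 800 possible allocation lists. If the ICUs are distributed otherwise, pair them by type across sequences.

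Add unit type to the interim model and unit type by phase to the final model. The model terms alone restore most of the type I error protection against ICU imbalance. The stratified allocation adds precision and visible balance.

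The cost is a revised allocation list and two model terms. No extra units, devices or data are needed. The allocation part must be settled before devices are deployed. The model terms can be added at any time before the interim data are examined.

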Prior research with automated disinfection systems focused on the terminal disinfection of isolation rooms only. This is a problem, as patients might be infected or colonized with an eiHAI but the eiHAI might not be detected during the hospital stay. This type of approach probably will likely “miss” certain rooms where a patient is a silent carrier of an eiHAI. This type of approach also results in a low daily use of such technologies and limits the global effect of UV disinfection on a hospital unit’s environmental hygiene. In the proposed project, the automated disinfection system (PX-UV) will be used following every discharge on participating units. This approach will significantly increase the frequency, breadth and impact of the intervention on study units in a way that has not been previously studied.

Use of sham device and double-blind status

The proposed study is also novel in its use of sham automated devices to provide a “placebo” intervention and facilitate control for many potential confounders associated with the implementation of automated disinfection devices on the study units, such as changes in general infection control awareness and practices and environmental hygiene. Additionally, all healthcare personnel (including device operators and environmental services staff), will be blinded to the intervention/sham status of the devices. In addition, the study personnel including the PI and individuals performing data analysis, will be blinded to the intervention/sham status of the devices. The device status will be written on a piece of paper by the manufacturer with the serial numbers of each device indicated, sealed in an envelope and kept in a secure location by the study statistician ([name]) for later retrieval when trial data analysis has been completed.

Use of crossover design

The crossover study design represents an improvement in study design quality compared with studies in the current literature and allows for the control of additional measured and unmeasured confounders. A crossover design, with each unit observed with both the active and sham intervention, means each unit serves as its own control, which will improve the precision of the comparison, reducing the number of units and total expense required for the study.

Notable differences from recent CDC-sponsored trial

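### The Aim 1 analysis opens with a carryover test that compares different units, is invalid in the named Poisson model if unit rates differ, and has no stated consequence

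*Combined protocol and SAP*

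**What the plan says.** The Statistical Analysis section, Aim 1, puts a carryover test first: "Analysis will begin with testing for a carryover effect, but the long 6-month washout is expected to make carryover unlikely". No test form, significance level or action on a positive result is given.

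The model is named in the same paragraph: "The primary analysis will use a Poisson regression model to compare PX-UV disinfection with sham disinfection". Its listed terms are all at patient level: "The primary regression model will include patient age, sex, race and indicator variables for co-morbid conditions". No unit, hospital, phase, sequence or overdispersion term is named, and none is excluded.

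Under Clinical Sites, devices "will be assigned randomly to the units in Phase 1 and then switched in Phase 2", within each hospital. The 16 units are mixed, "including two medical intensive care units (ICUs), two surgical ICUs and 12 non-ICU medical-surgical wards". Under Use of crossover design, the design is justified because it "means each unit serves as its own control, which will improve the precision of the comparison".

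**The concern.** With two sequences and two phases, carryover cannot be separated from a difference between the two sequence groups. The test therefore sets the both-phase totals of about eight units against those of about eight other units. Any ordinary difference between units enters that contrast in full. A Poisson standard error with no unit term treats such a difference as if it could only be carryover. A fixed unit term would make carryover inestimable. A random unit term would make the test valid but weak.

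The plan's case for a crossover is the within-unit comparison. An opening test that ignores clustering could cast doubt on that comparison without cause. If a positive result sent the analysis back to Phase 1, the trial would rest on a between-unit comparison with half the data, and one already examined at the 12-month interim analysis.

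**Working it through.** **Inputs from the documents.** 16 units; 89,790 eligible days in 24 months, so 44,895 per arm; rates 3.2 and 2.208 per 1000 eligible days (rate ratio 0.69); final alpha 0.049; 287 events expected if nothing changes (Sample size estimation; Clinical Sites). **Assumed:** eight units per sequence, equal unit sizes, between-unit CV of the true rate 0 to 0.5.

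**The plan's own figure.** A two-sided test of proportions with 44,895 days per arm at alpha 0.049 gives power 0.814. The stated 81% is reproduced.

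**False-positive rate of the carryover test, Poisson standard error.**
- Events per unit per phase: m = 0.0032 × 44,895 / 16 = 8.98.
- Each sequence-by-phase cell has 8 × 8.98 = 71.8 events. The contrast is the sum of log rates over both phases, one sequence minus the other. Its Poisson variance is 4 / 71.8 = 0.0557.
- A unit effect that is stable over both phases adds 2 × 4 × CV²/8 = CV².
- Variance inflation: V = 1 + CV²/0.0557 = 1 + 17.96 × CV².
- True size of the nominal 5% test: 2Φ(−1.96/√V).

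| CV | V | False-positive rate |
|---|---|---|
| 0 | 1.00 | 5% |
| 0.2 | 1.72 | 13.5% |
| 0.3 | 2.62 | 22.6% |
| 0.4 | 3.87 | 31.9% |
| 0.5 | 5.49 | 40.3% |

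Simulation with no carryover and no treatment effect agrees (about 13%, 23%, 32% and 40% at CV 0.2 to 0.5).

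**If a positive test led to Phase 1 only (assumed).**
- Identical units: the pre-test is independent of the within-unit contrast but has correlation 1/√2 = 0.71 with the Phase 1 test. Overall type I error = 0.95 × 0.049 + P(both the pre-test and the Phase 1 test reject) = 0.0466 + 0.0167 = 0.063.
- Poisson standard errors: 9.5%, 14%, 20% and 27% at CV 0.2, 0.3, 0.4 and 0.5 (simulated).
- The same rule with unit-level t tests at every step: 5.9%, 6.5%, 6.4% and 7.0% at CV 0, 0.2, 0.3 and 0.5. Pre-testing itself therefore adds about 1 to 2 points; the rest is clustering.
- Power at rate ratio 0.69, Poisson standard errors: 78%, 75% and 71% at CV 0.2, 0.3 and 0.5, against 80-81% if the within-unit contrast is always used. With unit-level tests the loss is only about 1 point. Phase 1 alone has about 52% nominal power.

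**Could a valid carryover test gate the analysis?** A t test on unit totals (14 degrees of freedom) holds about 5% error. Take carryover of half the log effect, so that the sham rate after UV is multiplied by √0.69 = 0.83. Its power is then about 12% at CV 0 and 7-9% at CV 0.2 to 0.4.

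**Does the within-unit Poisson test hold its level?** Only if unit rates are stable between phases. With unit CV 0.3 and an assumed unit-by-phase CV of 0.2 or 0.3, its type I error is about 9% or 15%.

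**The case against.** The strongest objection is that the harmful step is not in the plan. A reader might infer that a positive carryover test discards Phase 2. The documents do not support that. The trial is sized on all 24 months, the final criterion of 0.049 is stated without condition, and the only Phase 1 test mentioned is the interim analysis. The opening test may be meant as a diagnostic. This stands, so every two-stage figure is conditional.

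Second, the between-unit CV is not given. Age, sex, race and co-morbidity terms could absorb part of the ICU-to-ward difference, and choosing units for high recovery of these organisms may narrow the spread. The plan also does not rule out a unit term. This stands too: the 14-40% is a range over an assumption. Even so, a CV of zero is implausible for four ICUs and 12 wards in two hospitals.

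Third, the larger error rates mainly measure ignored clustering rather than pre-testing. That is correct, as the unit-level results show.

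What the objection does not remove is that the plan names an opening test that is invalid in its own listed model if units differ, and leaves open what a positive result would do to the primary analysis.

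**Conclusion.** The point holds in a conditional form. As written, the carryover test is a between-unit contrast in a model that lists nothing to absorb unit differences. Its false-positive rate is about 5% with identical units and about 14% to 40% at an assumed CV of 0.2 to 0.5, taking unit effects as stable across phases and not explained by the patient covariates.

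If it gated the analysis, overall type I error would be about 6% at best. The 10-27% figures need both the assumed Phase 1-only rule and Poisson standard errors, and should not be read as properties of this plan. Nor should a reader infer that deleting the carryover sentence alone secures the nominal 4.9% level, because unit-by-phase variation would inflate the within-unit Poisson test as well. A valid carryover test is too weak to reassure when negative. The protection in this design is the 6-month washout.

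**What to change.** Replace the carryover sentence with a statement that the primary analysis is the both-phase, within-unit comparison, with unit and phase terms and standard errors that allow for unit-by-phase variation, whatever the carryover estimate. Report carryover afterwards as a descriptive estimate with a unit-level confidence interval, and rely on the washout.

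The cost is a short change of wording before unblinding and no extra data. Standard errors that allow for clustering may lower power below the planned 81%. The other downside is that real carryover would not formally change the primary analysis. With carryover of half the log effect, the within-unit log rate ratio shrinks to (2 × log 0.69 − log 0.83)/2 = 0.75 × log 0.69, a rate ratio of about 0.76. Power is then about 55%, against about 59-61% for the two-stage rule with Poisson standard errors, which has the inflated error shown above. The plan itself regards that situation as unlikely after six months.

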Investigators examined the impact of PX-UV on nosocomial *C. difficile* and VRE infection rates. PX-UV disinfection was evaluated in three patient units (intervention arm), while three units with similar baseline CDI rates and patient populations served as controls. The intervention and control arms each included two Hematology/Oncology units and one Medical-Surgical unit. Patient rooms on the intervention units received PX-UV in three 5-minute positions after standard terminal cleaning. Infection control measures (i.e. bleach use, hand hygiene and isolation compliance rates) were similar in the two study arms. CDIs, diagnosed by polymerase chain reaction (PCR), were classified as HAIs and attributed to the unit if CDI was diagnosed > three days after admission or within four weeks of dismissal from that unit. Incidence rates expressed as the number of HAI CDIs per 10,000 patient-days were analyzed using a negative binomial regression model. Within units of the intervention arm, 85% of rooms were disinfected with PX-UV. Baseline HAI CDI rates in the intervention and control arms were not significantly different (18.3 and 20.1 per 10,000 patient-days, respectively [p=0.28]). During the 6 month period of PX-UV disinfection, the HAI CDI rate in the intervention units decreased to 11.2 per 10,000 patient-days compared to an increase to 28.7 per 10,000 patient-days in control units (p=0.03). The rates of HA-VRE for the control units were 1.91 at baseline and 1.96 at completion of the study (p=0.363). The rates of HA-VRE for the intervention units were 3.25 at baseline and 1.23 at completion of the study (p=0.016).³² Thus, in the PX-UV arm, there was a 38.8% decrease in *C. difficile* rates, while rates increased by 42.8% in the control arm.

Recovery of Genetically Identical VRE Strains

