Inclusion Criteria: All patients admitted to the study units will be eligible. Only patients who remain in the hospital for four calendar days or longer will be eligible for evaluation of eiHAI outcomes (the day of admission counts as calendar day one). Patients who do not develop an eiHAI at the time of unit discharge will be eligible for eiHAI outcomes for up to calendar 3 days following unit discharge.

Data Collection and Treatment Outcomes

Variables that are attributes of patients:

- *C. difficile* laboratory test results: hospital-acquired *C. difficile* will be defined as a laboratory-positive PCR test on calendar day 4 or beyond on the study unit; or within 3 days after discharge from unit.²⁸
- Clinical cultures positive for VRE, MRSA, ESBLs or *A. baumannii* on day 4 or beyond on the study unit; or within 3 days after discharge from unit.²⁸
- ICD-9 and ICD-10: primary and secondary *ICD-9* and *ICD-10* diagnoses.
- Patient demographics: age, gender, insurance status and zip code.
- Admission and transfer information: admission source and admission and discharge dates for both the study units and the entire episode of care, including room numbers.
- Antibiotic use: the dose, duration and type of antibiotic prescribed to the patient on the study units
- Infections and colonizations due to eiHAI as well as other pathogens, defined according to National Healthcare Safety Network (NHSN) criteria.³⁹
- PX-UV disinfection status: sham/intervention disinfection occurring before patient is admitted to the room.

Variables that are attributes of the unit: For unit-level variables that are measured monthly, the value used for each patient will consist of the average of the immediately previous and immediately following values for the variable, each weighted by the number of days from the mid-point of the patient stay on the unit.

- Hand Hygiene compliance: monthly measures of hand hygiene compliance according to standard infection control guidelines and also according to “secret observers” who are members of the study team. Approximately 30 observations will be performed each month on study units.

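### The Phase 1 efficacy stop compares 8 units with 8 other units on a model that names no unit variation, so its 0.003 level holds only if units do not differ

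*Combined protocol and SAP*

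**What the plan says.** Under Hospital Unit Selection and Clinical Sites, 16 hospital units (4 ICUs and 12 wards) are randomised within two hospitals. Half receive PX-UV and half sham in Phase 1, and they switch in Phase 2. The case for the crossover, under Use of crossover design, is that observing each unit on both devices "means each unit serves as its own control, which will improve the precision of the comparison".

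Under Statistical Analysis, Aim 1, the primary analysis is a Poisson regression. "An interim analysis for efficacy will be made after the first 12-month intervention period using an O'Brien-Flemming boundary", and "the trial may be halted for efficacy if a chi square statistic of 8.78 or greater is observed for the interim test" (p ≤ 0.003). After that look, "the p-value for the test at end of the study will need to be 0.049 or lower to be significant".

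On model terms: "The primary regression model will include patient age, sex, race and indicator variables for co-morbid conditions". No unit term, random effect, dispersion parameter or robust variance is named for either look, and no separate interim model is given. Data Collection and Treatment Outcomes explains how unit measures are attached to patients ("For unit-level variables that are measured monthly, the value used for each patient"), but the analysis section does not place them in the primary model. It says instead: "Secondary analysis will summarize and compare study arms (and periods) on: administered antibiotic doses and types, hand hygiene compliance". Sample size estimation approximates Poisson power by a binomial test of proportions, which has no unit component.

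**The concern.** After Phase 1 each unit has had one device type only. The contrast is wholly between units, and the own-control property that justifies the design does not yet exist. A fixed effect for unit could not restore it, because device is nested in unit at that point. If units differ in infection rate beyond what the patient covariates and hospital explain, a chance imbalance in which units drew PX-UV looks like a device effect. A Poisson variance does not allow for this.

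A false stop would cancel Phase 2. That would remove Aim 1.2, the same-ward comparison across phases, which is the analysis able to separate unit differences from the device.

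**Working it through.** **Inputs from the documents.** 89,790 eligible days, 44,895 per arm, and rates of 3.2 and 2.208 per 1000 (Sample size estimation); 287 events if past rates continue, 16 units randomised within hospital (Clinical Sites); half the units on each device (Aim 1, Method 1).

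**Assumed.** Equal units, equal phases, no device effect, unit rates stable over time, residual between-unit CV of 0.1, 0.2, 0.3 or 0.5.

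**1. The plan's own figures.** Lan-DeMets O'Brien-Fleming-type spending, one-sided 0.025 at half the information, spends 2[1 − Φ(2.241/√0.5)] = 0.00153. That gives z = 2.963, chi-square 8.78, two-sided p = 0.00305 and final p = 0.0490. All three stated values reproduce. The 50% fraction is inferred from them; the plan does not state it. Power also reproduces: 81.4% by two proportions at alpha 0.049, and 80.9% on the Poisson log-rate scale.

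**2. What crosses.** Phase 1 has 287/2 ≈ 144 events, or m = 287/32 = 8.97 per unit. With equal exposure the Poisson comparison without covariates is (A − B)²/(A + B), used here in place of the planned test. Crossing needs |A − B| ≥ √(8.78 × 144) = 35.6, about 90 events against 54.

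**3. Effect of unit variation.** The variance of A − B is inflated by 1 + m·CV², so the chance of crossing is 2[1 − Φ(2.963/√(1 + 8.97·CV²))]:
- CV 0.1: factor 1.09, z 2.84, 0.45%
- CV 0.2: factor 1.36, z 2.54, 1.1%
- CV 0.3: factor 1.81, z 2.20, 2.8%
- CV 0.5: factor 3.24, z 1.65, 10.0%

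**4. Simulation** (gamma-distributed unit rates, Poisson counts, 200,000 replicates per row; the final look uses both phases at 0.049):

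| Residual CV | Crosses 8.78, either direction | Crosses favouring PX-UV | Two-look type I error |
|---|---|---|---|
| 0 (as planned) | 0.3% | 0.15% | 5.0% |
| 0.1 | 0.4% | 0.2% | 5.1% |
| 0.2 | 1.1% | 0.5% | 5.5% |
| 0.3 | 2.7% | 1.3% | 6.9% |
| 0.5 | 9.7% | 4.8% | 13.5% |

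In every row the final test alone stays near 4.9 to 5.0%, because stable unit differences cancel once each unit has had both devices.

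**5. Within-hospital randomisation.** Suppose ICU versus ward is the only difference and the ICU rate is 1.8 times the ward rate (CV 0.29). The chance of crossing is 2.8% with two ICUs at each hospital and 1.7% with all four at one. At 1.5 times it is 1.1% and 0.8%. These ratios are assumptions, and the documents do not say where the ICUs are.

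**6. A unit-level rule.** The interim look is a t-test on log(count + 0.5) per unit (14 df) at p ≤ 0.003. The final look is a t-test on unit phase differences between sequences (14 df) at p ≤ 0.047, and 0.003 + 0.047 = 0.05. Total type I error is 4.5 to 4.8% over between-unit CV 0 to 0.5 and unit-by-phase CV 0 to 0.3. If only the interim test is changed and a plain Poisson final test is kept at 0.047, total error is about 9 to 10% at an assumed unit-by-phase CV of 0.2.

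**The case against.** The strongest reply is that the plan is silent rather than wrong. It says what the model will include, not that nothing else will enter. The list also omits treatment, period and person-time, so it cannot be complete. The carryover test and Aim 1.2 imply some period and within-ward structure. This stands to the extent that the plan does not forbid a unit-aware variance. It does not rescue the interim look: the carryover test and Aim 1.2 both need Phase 2 data, and neither puts unit variance into a Phase 1 test. The stated 0.003 still has no basis unless units are alike.

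Second, the size rests on a CV that the documents do not give. That stands. Only variation left after patient covariates and within-hospital randomisation counts, and choosing units for relatively high recovery may have narrowed their spread. Pre-trial unit rates could remove more. If all organisms were recorded over the same 8 months (not stated), there would be about 1.3/1000 × 123 × 243 × 2.5 ≈ 97 events, 6.1 per unit. With perfectly stable rates, adjustment could then remove up to CV²/(CV² + 1/6.1), about 6, 20, 35 and 60% of the between-unit variance.

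Third, the rule permits a halt and does not require one. That stands too: the figures describe crossing the boundary.

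Fourth, the earlier unit-based PX-UV study in the preliminary work was analysed differently ("Incidence rates expressed as the number of HAI CDIs per 10,000 patient-days were analyzed using a negative binomial regression model"). It compared parallel units without crossover. It shows that a dispersion term is a familiar choice, not that this trial's counts are overdispersed.

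**Conclusion.** The concern holds. The boundary value is correct for independent events, but the variance behind the interim test is not specified in a way that supports it. Any residual unit variation raises the crossing probability above plan; the amount depends on an unknown CV. One-sided figures should be set against 0.15% and two-sided figures against 0.3%.

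Three stronger readings are tempting, and the documents do not support them:
- A reader might infer that 8.78 or 0.049 was miscalculated. Both reproduce.
- A reader might infer that the trial's overall false-positive rate is badly inflated. With stable units it reaches only about 5.5% at CV 0.2, and clear inflation needs a CV of 0.3 or more, which nothing in the documents establishes.
- A reader might infer that the final test is invalid as well. That needs unit rates that move between phases, a second quantity the documents do not give. It is a reason to choose the final variance with care, and it adds nothing to the severity of the interim problem.

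**What to change.** 1. Base the interim stop on a test that includes between-unit variance with small-sample degrees of freedom, such as a unit-level comparison of rates on about 14 df. Keep p ≤ 0.003 there and use 0.047 at the end. This split needs no advance knowledge of the CV. Adjustment for pre-trial unit rates, if available for all organisms, is a reasonable addition.
2. State a final variance that also respects units: within-unit phase contrasts compared between sequences, or unit and phase effects with estimated dispersion.
3. Restate power for the final test chosen.

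The cost is more than wording. Under the planned 31% reduction at CV 0.2, the unit-level rule stops early for PX-UV about 6% of the time, against about 20% for the stated rule. Power for unit-level log differences is about 72 to 62% over CV 0 to 0.5 with equal, stable units, against the stated 81%. At an assumed unit-by-phase CV of 0.2 it is about 60 to 52%. Unequal unit sizes lower it further, and a weighted or estimated-dispersion version is then preferable. The sponsor should decide with these figures in view whether the present size is enough. Dropping the interim look is an option, not a requirement.
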